The main objective of this clinical trial is to test the efficacy of two different transcranial electrical stimulation techniques (tES) to modify dysfunction of central modulatory mechanisms of pain, and to improve symptoms and quality of life in refractory chronic pain patients.

In this vein, we hypothesize that transcranial electrical stimulation procedures will be more effective than sham to improve pain and related symptoms. Besides, central biomarkers of pain processing and modulation (i.e., CPM, TSSP and EEG) will be useful to predict the patient response to treatment and thus, the efficacy of these tES procedures.

Based in these principal ideas, we propose the following secondary or specific objectives:

- A. To analyse the relationship between the studied biomarkers and clinical pain characteristics of patients (intensity, location, frequency, duration, daily interference caused by pain).
- B. To stratify patients and propose profiles based on the selected biomarkers, which may be useful to improve diagnosis and to guide individualized treatment plans.
- C. To develop home-based treatment schemes for patients with refractory chronic pain. We will assess if tES procedures are safe, feasible and acceptable for the at-home management of this medical condition.
- D. To test if tES techniques are self-manageable by patients and to observe the impact of this treatment in the caregiver-burden declared by the reference person.
- E. To test the efficacy of tDCS (Direct current) versus tACS (Alternant current) to modify dysfunction of central endogenous analgesia (i.e., CPM and TSSP) and to reduce pain and related symptoms in the patients, in a placebo-controlled clinical trial.
- F. To analyze how the different tES techniques (tDCS and tACS) affect brain oscillatory activity, and to test if the changes in oscillatory activity are related to pain relief.
- G. To test the power of the biomarkers/patients' stratification to predict treatment efficacy and to identify the characteristic of best responders patients.

- H. To assess the effect of sex/gender and other modulator variables (age, disease duration, medication, lifestyle, mood...) on all the analyses (central biomarkers, patients' stratification, response to treatment...).

3. Study design

The research is classified as a double-blinded, randomized clinical trial with one control group which receive a sham stimulation.

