The transcranial electrical stimulation intervention is considered the independent variable, which contains three different conditions or categories differentiated by the type of stimulation used. These conditions define the three groups of treatment:

- 1) Transcranial direct current stimulation (tDCS), which induces a continuous current over the left primary motor cortex (M1). Current intensity is set at 2mA and it is applied for 20 minutes, with ramp-up and ramp-down of 15 seconds at the beginning and end of the stimulation period.
- 2) Transcranial alternat current stimulation (tACS), which induces an alternant current over somatosensory cortical region. Current intensity is set at 10-Hz and it is applied for 20 minutes, with ramp-up and ramp-down of 15 seconds at the beginning and end of the stimulation period.
- 3) Sham stimulation, which acts as a placebo-control group. It uses the same montage as the previous ones, but it does not emit any kind of current. The position of electrodes will be similar to the previous conditions, but the current will be just activated during the ramp-up and ramp-down moments.

Chronic pain patients are randomly assigned to one of these groups, although the active stimulation conditions agglutinate the 80% of sample (40% tDCS; 40% tACS), whereas the control group contains by the remaining 20%.

As dependent variables, we consider the assessed clinical symptoms, mainly pain characteristics (including intensity, location, frequency, duration and daily interference caused by pain), fatigue, depression/anxiety, sleep quality, physical functioning and life quality, following the guidelines proposed by the *Initiative on Methods, Measurement, and Pain Assessment in Clinical Trials* (IMMPACT; Dworkin et al., 2005).

Besides, as far as we aim to assess the efficacy of tES techniques to restore the potential dysfunctions in processing and modulation of pain in patients, central biomarkers as Conditioned Pain Modulation (CPM), Temporal Summation of Second Pain (TSSP) and EEG are also included as dependant variables. Thus, we try to identify any change in these variables which could be attributable to the intervention.

The intervention and evaluation protocols are more in-depth defined in the following sections.

4. Sample and recruitment

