Besides, we will conduct simple ANOVA analyses to compare these indexes of pain processing and modulation (CPM, TSSP, EEG) between specific groups of patients, divided by type/origin of chronic pain and sex. We reserve the possibility of making *Cluster analyses* in the basis of the mentioned central biomarkers, following by an ANOVA comparison of clinical features between the emerged groups.

Besides, participants will be classified into CPM and TSSP respondents or non-respondents taking into account their results in these sensory tests. Those patients who report a significant increment in pain thresholds will be considered respondents; whereas the opposite applies for TSSP, as it must be detected a significant increase in perceived pain intensity in the last pulse compared to the first one. Depending on the proportions observed, it could be useful to divide TSSP respondents based on the degree of the pain sensitization. Regarding this sample division, we can compare the clinical profile of respondents and non-respondents patients using *Chi square statistic*.

As far as intervention efficacy is concerned, qualitative analyses will focus on differentiating the patients who effectively respond to treatment (Treatment-respondents) from those who do not improve (Non-treatment-respondent). Respondents are those

participants whose improvement in a certain clinical variable are equal or higher than the 30%; whereas non-respondents are all those who do not comply with this criterion. This variation is extracted from the comparison of pre- and post-treatment measurements.

Therefore, for each of the endpoints, we will obtain a number/percentage of respondents and non-respondents. Using the *Chi-square test*, we will compare the proportion of respondents between treatment groups to identify the most efficacious stimulation procedure. A separated analysis will be done for each described endpoint, which define what a respondent is.

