The main quantitative statistical analyses to assess the efficacy of transcranial electrical stimulation techniques consist of ANOVA-tests of repeated measures with three groups. Time-measures for each of the above-mentioned endpoints are taken as intragroup variables (pre vs. post), whereas intergroup measures refer to the received stimulation or treatment (tDCS vs. tACS vs. Sham). Thus, both clinical variables (for example, pain intensity, fatigue, sleep quality, disease severity and interference) and potential biomarkers (including brain oscillatory activity registered by EEG, CPM and TSSP response) are considered as intragroup variables.

Those covariates which show a significant correlation with clinical outcomes will be also included in their correspondent ANOVA analysis. These potential covariates are basically age, self-perceived stress, social support, catastrophism and medication intake.

All these statistical analyses will be repeated in separated groups of patients, created in the basis of sex, type and duration of chronic pain, among other characteristics. The objective is to assess whether the clinical outcomes depend on sex or diagnosis, as each tES could be more effective for specific diseases.

CPM/TSSP response and EEG pattern observed before the tES application are also regarded as potential predictors of the treatment efficacy. Thus, the pre-treatment indexes of these biomarkers will be used as independent variables in *Linear regression models*, which includes the clinical improvement in each endpoint as dependent measure. The procedure will be repeated with *Logistic regression analysis* establishing the respondent vs. no-respondent categories as dichotomic variable.

For last, we will register and assess the percentage of dropouts with their respective motives, in order to obtain an index of the feasibility of home-based tES approach. Client

satisfaction index and caregiver interview will also include questions about the capability of participants to manage with tES devices, data which will be qualitatively analysed.

8. Chronogram

WORKING PLAN (WP)		3	6	9	12	15	18	21	24	27	30	33	36
TASK	\ MONTH												
WP1. Development and selection of assessment and monitoring tools for refractory chronic pain patients													
Task 1.1.	Review of the literature and identification of the most common and important variables used as outcomes in clinical trials with chronic pain population.												

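### The main efficacy analysis designates no active-versus-sham contrast, efficacy term or multiplicity rule, so a significant three-group result need not show that either stimulation arm beats sham

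*Combined protocol and SAP*

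**What the plan says.** Section 2 states the hypothesis that "transcranial electrical stimulation procedures will be more effective than sham to improve pain and related symptoms". The comparison of the two active techniques appears among the secondary or specific objectives, as item E: "To test the efficacy of tDCS (Direct current) versus tACS (Alternant current".

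Section 7 says that the main quantitative efficacy analyses "consist of ANOVA-tests of repeated measures with three groups". The within-patient factor is pre versus post; for the between-patient factor the text reads "whereas intergroup measures refer to the received stimulation or treatment (tDCS vs. tACS vs. Sham". For responders (improvement of at least 30%), a chi-square test is planned in which "we will compare the proportion of respondents between treatment groups to identify the most efficacious stimulation procedure".

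On covariates, section 7 says: "Those covariates which show a significant correlation with clinical outcomes will be also included in their correspondent ANOVA analysis". It adds: "These potential covariates are basically age, self-perceived stress, social support, catastrophism and medication intake".

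Section 3 sets the allocation: "the active stimulation conditions agglutinate the 80% of sample (40% tDCS; 40% tACS", with the remaining 20% on sham. Of the 120 patients planned in section 4, that is 48, 48 and 24. Section 4 gives the only alpha in the document (0.01) and sizes the trial for the same three-group, two-measurement ANOVA. Its effect of 0.68 comes from a two-group comparison of active tDCS with sham.

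**The concern.** The hypothesis concerns each active technique against sham. The planned test asks whether the three arms differ anywhere. Section 7 does not say that group-by-time is the decisive term, that sham is the reference, which pairs will be tested, at what alpha, or with what correction. The responder chi-square has the same gap, and its stated purpose is to find the best procedure rather than to beat sham.

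The allocation sharpens this. Sham is the smallest arm, so tDCS versus tACS, the secondary question, is the most precisely estimated pair. A significant F can therefore arise without a demonstrated advantage over sham. The sham comparisons that test the hypothesis would then be selected, and corrected or not, once results are known.

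Two smaller matters sit in the same paragraphs. The pre/post ANOVA gives up precision that adjustment for baseline pain would recover. Admitting covariates by observed significance lets the model depend on the data and differ between endpoints.

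**Working it through.** **The plan's own figure.** Section 4 gives N = 21 for effect F = 0.68, alpha 0.01 and power 0.99. For the group-by-time interaction, λ = f²·N·m/(1−ρ), with df 2 and N−3. With m = 2 and ρ = 0.5 (assumed; the plan gives none), N = 21 gives λ = 0.4624 × 21 × 2/0.5 = 38.8 and power 0.994; N = 20 gives 0.990. So 21 reproduces as the size for the overall 2-df test, in equal groups of 7. It is not the size for a sham contrast.

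**Precision by pair (SD units, 48/48/24).** tDCS–tACS: √(2/48) = 0.204. Active–sham: √(1/48 + 1/24) = 0.250. Ratio 1.22, so a sham contrast has a standard error 22% larger.

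**Share of significant overall tests with no significant sham contrast.** Assumptions: 48/48/24, no dropout, equal pre and post variances, ρ = 0.3/0.5/0.7, group-by-time as the efficacy term, F on change scores (df 2, 117). Effects in the order tDCS, tACS, sham are d; on the change scale they become d/√(2(1−ρ)).

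Example, d = (0.68, 0, 0), ρ = 0.5: the weighted mean is 48 × 0.68/120 = 0.272, so λ = 48 × 0.408² + 72 × 0.272² = 13.3 and overall power is 0.91. The expected t is about 0.68/0.204 = 3.3 for tDCS–tACS but 0.68/0.250 = 2.7 for tDCS–sham. The shares come from simulation (200,000 trials per case for Holm at 0.05; 100,000 at 0.01). A repeat run agreed to within about one percentage point.

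| Truth | Alpha | Holm | Unadjusted pairs after significant F |
|---|---|---|---|
| 0.68, 0, 0 | 0.05 | 34/25/9% | 21/15/4% |
| 0.68, 0, 0 | 0.01 | 49/41/23% | 38/31/15% |
| 0.68, 0.34, 0 | 0.05 | 10/7/3% | 5/3/1% |
| 0.68, 0.68, 0 | 0.05 | under 1% | under 1% |
| 1.36, 0, 0 | 0.05 | under 1% | under 1% |
| 1.36, 0, 0 | 0.01 | 4/0.5/0% | no larger |

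The value 1.36 is 2 × 0.68, the standardised difference equal to f = 0.68 for two equal groups. At alpha 0.05, in the one-arm (0.68) and partial cases, tDCS–tACS is significant in at least 97% of the trials counted under Holm. Requiring the contrast to favour the active arm changes the first row to 35/26/10% and 24/17/6%.

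**Responders (assumed rates, alpha 0.05, Holm).** 50/20/20%: 32% of significant chi-square results have no significant favourable sham contrast. 50/35/20%: 9%. 50/50/20%: 0.5%.

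**Why a rule is needed.** With no true difference, ungated unadjusted tests at a nominal 0.05 give a family error of 8.5% (two sham contrasts) or 12% (all three pairs). At a nominal 0.01 the figures are 1.8% and 2.6–2.7%.

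**Precision, one sham contrast.** Noncentral t, 48 v 24, d = 0.68, two-sided 0.05. The effect is 0.68/√(2(1−ρ)) for change scores (df 70) and 0.68/√(1−ρ²) for ANCOVA (df 69).

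| Baseline SD / post SD | ρ = 0.3 | ρ = 0.5 | ρ = 0.7 |
|---|---|---|---|
| 1 | 0.62 v 0.80 | 0.77 v 0.87 | 0.93 v 0.96 |
| 0.7 (assumed) | 0.74 v 0.80 | 0.86 v 0.87 | 0.96 v 0.96 |

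The second row uses √(1 + 0.7² − 1.4ρ) as the SD of change. It allows for section 4's entry thresholds on pain, which may narrow the baseline spread.

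**Covariate screen.** With n = 120 and an assumed 0.05 threshold, a covariate truly correlated 0.1, 0.2 or 0.3 with the outcome enters in about 19%, 60% or 91% of trials.

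**The case against.** The strongest reply is that the plan's intent is clear. The hypothesis points to sham, objective E goes on to place the tDCS–tACS comparison within a placebo-controlled trial, there is one primary endpoint, and any analyst would follow a significant F with pairwise tests. This stands as far as intent goes. It does not settle which pairs are confirmatory, at what alpha, or with what correction.

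The size can also be challenged, and much of that stands:
- The largest shares need one arm with exactly zero effect, whereas the hypothesis speaks of both procedures. If both work equally the share is under 1%.
- They need 0.68 to be a standardised mean difference. The plan labels it F, and N = 21 reproduces with it as Cohen's f. The documents cannot settle what the cited meta-analysis measured.
- Holm after a significant F is stricter than necessary. With three groups, unadjusted pairwise tests gated on the F also control the family error. The plan does not state that procedure, but it lowers the shares.

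A reader might infer from section 6.1, which treats the pre-post difference as the index of efficacy, that uncontrolled change would be taken as proof. The documents do not support this: section 7 goes on to compare the arms, and group-by-time is the natural reading. The term still needs naming.

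**Conclusion.** The gap is real. Neither efficacy analysis in section 7 designates a test of the section 2 hypothesis, and a significant three-group result at 48/48/24 need not show that either active arm beats sham. How often this would matter runs from almost never (both arms equally effective) to between about a tenth and a half of significant trials under Holm (one arm effective at an SMD of 0.68, depending on ρ and alpha). It is at most about 4% if 0.68 is Cohen's f. All of this rests on an assumed ρ, equal variances and no dropout.

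Two stronger readings are tempting and should be resisted. First, that the plan would produce false efficacy claims: in every scenario in the table tDCS truly beats sham, so the affected trials fail to demonstrate a real effect. Second, that the pre/post ANOVA is invalid: its group-by-time test is a valid comparison of change scores. Baseline adjustment is a gain in precision only, small if the baseline spread is narrow and immaterial if 0.68 is an f.

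**What to change.** In section 7:
- Make the primary analysis an ANCOVA of the 15-day post-treatment mean pain NRS on arm and the 15-day baseline mean.
- Pre-specify tDCS–sham and tACS–sham as the two primary contrasts, at a stated two-sided alpha and with a stated rule (Holm, Dunnett, or pairwise tests gated on the omnibus F). Make tDCS–tACS secondary.
- Use the same contrasts for the responder analysis.
- If the ANOVA is kept, name group-by-time as the efficacy term and add the same contrasts.
- Replace the significance screen with one fixed list of baseline covariates that the trial plans to measure.

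The cost is mainly wording, since Table 1 already plans both 15-day averages. One exception: section 6.2 names no instrument for perceived stress or catastrophising, so each needs one named or should be left off the list.

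There is a statistical price. If only one arm works (SMD 0.68, alpha 0.05, ρ = 0.3/0.5/0.7), the omnibus test rejects more often than ANCOVA with two Holm-corrected sham contrasts: 0.78/0.91/0.99 against 0.71/0.80/0.94. It answers a different question, though. The order reverses for a partial second effect (0.54/0.69/0.90 against 0.72/0.81/0.94) and when both arms work equally (0.60/0.75/0.93 against 0.83/0.89/0.97).

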activity, the spectral power of the oscillations and inter-site phase connectivity (Ploner et al., 2017). Secondly, we will analyse wave components of the contact heat evoked potentials (CHEPs) to obtain a neural correlate of the painful stimuli processing. For last, in order to study the modulatory role of attention in pain perception, we propose to obtain the evoked potential derived from a TSSP protocol, both paying exclusive attention to pain and during a simple cognitive task.

Besides, we will repeat the same procedure of quantitative sensory testing to ascertain its reliability. Finally, the following questionnaires will be used to get an accurate measure of some key symptoms and problems which usually accompanies chronic pain:

- Hospital Anxiety and Depression Scale (HADS; Cabrera et al., 2015). It represents a really useful tool to assess mood state and screen for depressive or anxiety disorders, which frequently cooccurs with chronic pain.
- Modified Fatigue Impact Scale (MFIS; Duarte et al., 2017; Kos et al., 2005), which accounts for the physical, emotional and social components of fatigue. Fatigue usually accompanies chronic pain conditions and results in great limitations for the daily functioning of patients.
- Pittsburgh Sleep Quality Index (PSQI; Macías & Royuela, 1996). This inventory inquiries into several areas about the sleep patterns, such as the related disorders, the self-perceived quality or the time passed until falling asleep.
- Zarit Burden Interview (Martín et al., 1996). This instrument is used with the principal caregivers of the patients to assess the stress and negative feelings associated with the caring tasks. Thus, it represents the core of the evaluation protocol for caregiver, and it intends to pay attention to this figure but also to add information about the patient autonomy.

In sum, all the proposed questionnaires assess relevant clinical variables which are expected to be improved by tES treatment. Therefore, changes observed in them between pre- and post-evaluation will be subjected to statistical analysis and taken as efficacy indices of treatment.

However, there are some other variables which, despite not expecting to be modified, could influence the treatment outcomes for better or worse. We refer to social support, self-perceived stress, catastrophizing thinking and beliefs about controllability of pain

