(Adams & Turk, 2015; Keefe et al., 2004; Jensen et al., 2011). Thus, these factors must be taken into account when assessing the efficacy of tES intervention and we intend to account them as covariates in statistical analysis.

Changes observed in criteria variables between pre- and post-evaluation must be equal or higher than the 30%, in order to ensure their clinical significance. It means that the improvement observed in self-reported questionnaires and in sensory testing (except for EEG) have to achieve or surpass the 30% of the original outcome. The direction of these differences depends on the specific scale; for example, it is expected a reduction in the global MPI score after treatment, but also a rise in pain thresholds. In the case of EEG, the analysis pre-post treatment are only subjected to the statistical significance. However, changes in brain activity patterns attributed to the tES will be tried to relate with improvement in clinical features.

Although all explained measurements are considered as success criteria of treatment, we selected pain intensity as the primary end point, taken as the average obtained from daily numerical rating scale. In this sense, participants will be classified into responders when they report, at least, a 30% decrease in their pain intensity. The rest of the variables are taken as secondary end points and are also regarded as treatment-efficacy indexes, basically the pain thresholds, life quality, physical functioning, interference caused by pain, pain unpleasantness, sleep quality, depression/anxiety, fatigue, caregiver burden and CPM/TSSP responses.

Table 1: End points of the clinical trial and their respective evaluation instruments

End points		Assessment tools
Primary end point	Pain intensity	Numerical Rating Scale of eleven points (0-10 NRS). Average obtained from daily self-reports during the fifteen days before treatment and the fifteen days after treatment.
Secondary end points	Global severity of chronic pain syndrome	Global and subscales scores of Multidimensional Pain Inventory (MPI).
	Interference caused by pain in daily living	Subscale score of Multidimensional Pain Inventory (MPI). Numerical Rating Scale of eleven points (0-10 NRS). Average obtained from daily self-reports during the fifteen days before treatment and the fifteen days after treatment.

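### The covariates in each main efficacy ANOVA are chosen by their significance in the trial's own outcome data, although section 6.2 says they must be accounted for; one fixed baseline set should be named in advance

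*Combined protocol and SAP*

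**What the plan says.** Section 6.2 (Evaluation methods and assessment tools) lists factors that are not expected to change but could influence the result of treatment: "We refer to social support, self-perceived stress, catastrophizing thinking and beliefs about controllability of pain". It says that they "must be taken into account when assessing the efficacy of tES intervention and we intend to account them as covariates in statistical analysis". No significance condition is attached.

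Section 7 (Data analysis plan) says that the main quantitative efficacy analyses "consist of ANOVA-tests of repeated measures with three groups", with pre and post measurements, for each endpoint. It then gives the covariate rule: "Those covariates which show a significant correlation with clinical outcomes will be also included in their correspondent ANOVA analysis". The candidates follow: "These potential covariates are basically age, self-perceived stress, social support, catastrophism and medication intake". Next comes the subgroup instruction: "All these statistical analyses will be repeated in separated groups of patients, created in the basis of sex, type and duration of chronic pain".

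The primary endpoint falls under this rule. Section 6.2 says "we selected pain intensity as the primary end point, taken as the average obtained from daily numerical rating scale", and section 7 gives it no separate model.

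**The concern.** An efficacy model should be fixed before outcomes are known. Here the list of adjustment variables comes out of the outcome data, endpoint by endpoint. Section 7 leaves these matters open:

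- the significance level of the screen;
- whether the correlation is with the pre, the post or the change score;
- which visit supplies the covariate;
- whether the candidate list is closed;
- whether the screen is repeated in subgroups.

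Two things are at stake. The first is credibility: a reader cannot tell in advance which model will give the main result, and the text leaves several choices to the analyst. The second is comparability: effects on different endpoints, or in women and men, may be adjusted for different variables. The plan wants to learn whether outcomes depend on sex or diagnosis, and that comparison is weaker when the models differ for reasons of sample size alone.

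**Working it through.** **1. The plan's own figures.** The plan gives no figure for covariate adjustment. Its sample-size figure of 21 can be reproduced. With f = 0.68, alpha 0.01, three groups, two measurements and an assumed correlation of 0.5 between measurements, λ = 0.68² × 21 × 2 / (1 − 0.5) = 38.8, and the group-by-time test has power 0.994. That calculation contains no covariates, so it does not bear on this point.

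**2. The two sections side by side.**

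| | Section 6.2 | Section 7 |
|---|---|---|
| Condition for entry | none | significant correlation with the outcome |
| Social support, stress, catastrophizing | named | named |
| Beliefs about control over pain | named | not named |
| Age, medication intake | not in this list | named |

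**3. What the screen does at different sample sizes.** Inputs from the plan: N = 120 and about 70% women, so 0.7 × 120 = 84 women and 36 men. Assumptions: a two-sided screening level of 0.05, the same true correlation r in both sexes, and the screen redone in each sex.

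Smallest significant correlation: r_crit = t / √(t² + n − 2).

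- n = 120: 1.980 / √(3.92 + 118) = 0.179
- n = 84: 1.989 / √(3.96 + 82) = 0.215
- n = 36: 2.032 / √(4.13 + 34) = 0.329

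Entry probability (Fisher z): Φ[(atanh r − atanh r_crit) × √(n − 3)]. At r = 0.25, atanh r = 0.2554.

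- Women: Φ[(0.2554 − 0.2180) × 9] = Φ(0.34) = 0.63
- Men: Φ[(0.2554 − 0.3418) × 5.745] = Φ(−0.50) = 0.31

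| True r | Women | Men | Enters in exactly one sex |
|---|---|---|---|
| 0.20 | 0.45 | 0.21 | 0.45 × 0.79 + 0.55 × 0.21 = 0.47 |
| 0.25 | 0.63 | 0.31 | 0.63 × 0.69 + 0.37 × 0.31 = 0.55 |
| 0.30 | 0.80 | 0.43 | 0.80 × 0.57 + 0.20 × 0.43 = 0.54 |

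At r = 0.25, four mutually independent covariates give both sexes the same model with probability 0.45⁴ = 0.04.

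The only alpha in the plan is the 0.01 of the sample-size section. Screening at 0.01 raises the cut-offs to 0.280 (women) and 0.424 (men). At r = 0.25 the entry probabilities become Φ[(0.2554 − 0.2873) × 9] = 0.39 and Φ[(0.2554 − 0.4523) × 5.745] = 0.13. The probabilities fall, but the gap between the sexes remains.

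Unrelated covariates enter too. With five independent candidates at 0.05, at least one gets in by chance with probability 1 − 0.95⁵ = 0.226 per endpoint.

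**4. Type I error.** In simulated null trials (N = 120, arms 48/48/24, five independent covariates, r from 0 to 0.3) the mechanically screened model rejects in 4.8 to 5.2% at nominal 5%, and in about 1.0% at nominal 1%.

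**5. Power at N = 120.** Simulation of the change score, which is equivalent to the group-by-time test. Five independent covariates, active effect 0.6 SD, screening and testing at 0.05. The correlations and the effect are assumptions.

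| r of each covariate with change | Screened | Fixed set of five |
|---|---|---|
| 0 | 62.7% | 61.0% |
| 0.1 | 64.0% | 64.6% |
| 0.2 | 67.9% | 71.4% |
| 0.3 | 85.4% | 87.9% |
| 0.3, 0.3, 0.1, 0.1, 0 | 71.2% | 71.4% |

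The fixed set gains between 0.2 and 3.5 points when covariates are prognostic and loses 1.7 when none is. The standard error under screening runs from about 2.5% smaller to about 1.2% larger. With four covariates that correlate 0.4 with one another (effect 0.72 SD), the difference vanishes: 0.815 v 0.813 at r = 0.15, 0.838 v 0.837 at r = 0.25, and 0.862 v 0.861 at r = 0.30.

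**The case against.** The strongest reply is that nothing invalid follows. Section 6.2 states an intention and section 7 can be read as saying how it will be carried out. Section 7 introduces its candidates as the main ones rather than a closed list, so control beliefs are not clearly excluded. The responder chi-square test on the primary endpoint uses no covariates and is untouched. Much of this stands: the conflict is one of wording, and the omission of control beliefs is a mismatch to reconcile, not a proven decision. But a rule that depends on significance does not carry out an unconditional commitment, and no other part of the plan fixes the set.

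A reader might infer three stronger things that the documents do not support.

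- **The screen inflates false positives.** Applied mechanically, it does not (step 4). If an analyst tried six readings that the text allows (pre, post or change score, screened at 0.05 or 0.10) and reported the most favourable, simulated type I error would be 5.5% at r = 0 and 8.7% at r = 0.30. That is a worst case, and the plan does not say that anyone will do this.
- **The screen gives up precision.** Not in general. The plan reports no correlations, the gain at N = 120 is small, and it disappears when the covariates are inter-correlated, as psychosocial scales may well be. A covariate related to the level of pain but not to its change does not affect the group-by-time test at all.
- **The sexes will get different models.** Section 7 repeats the analyses in subgroups but does not say that covariates are re-selected there. The divergence is an inference.

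**Conclusion.** The point holds as one of pre-specification and consistency. Two facts rest on the text alone: the covariate set of every main efficacy ANOVA, including the primary one, is decided from outcome data endpoint by endpoint, and this departs from section 6.2.

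The size of the between-sex divergence rests on assumptions: re-selection within sex, a screening level of 0.05 and true r = 0.25 in both sexes. A covariate then enters in exactly one sex about 55% of the time. The 4% figure for identical models also needs the covariates to be mutually independent.

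Power is not the reason to change: the difference at N = 120 is about 0 to 3.5 points in favour of a fixed set if covariates are independent and prognostic, and about zero if they are inter-correlated. The amendment is worth making because it is cheap and removes a choice that would otherwise be made after the outcomes are seen.

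**What to change.** In section 7, replace the significance screen with one fixed set of pre-treatment covariates, used for the primary endpoint and every other endpoint whatever the observed correlations. Specifically:

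- Reconcile the list with section 6.2: age, stress, social support, catastrophizing and control beliefs. Give the instrument and visit for each; section 6.2 names no scale for stress or catastrophizing.
- State explicitly whether pre-treatment medication is in the set. Section 7 names medication intake, and deleting the screen must not drop it silently. The daily survey also records medication use after treatment starts, so the time point must be given.
- Say in advance what happens when a covariate is part of the endpoint. Section 6.2 describes the Multidimensional Pain Inventory as covering perceived control and support, and Table 1 makes its global and subscale scores secondary endpoints.
- For the sex and pain-type questions, use the same set in every group, preferably through a treatment-by-group term in the full sample.
- Report the unadjusted model as a sensitivity analysis.

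The cost is mainly wording, plus up to five of 120 − 3 = 117 error degrees of freedom, or more if medication is added. If none of five covariates is prognostic, simulated power falls by about 1 to 2 points at N = 120. Fitted in the 36 men alone, where 5 of 33 degrees of freedom go, it falls by about 8 to 9 points (0.778 unadjusted to 0.687). That figure uses an effect of 1.35 SD, set to give men adequate power. At 0.6 SD the fall is about 3 points (20.9% to 17.8%), because power there is low under any rule. This cost is a further reason to prefer the interaction term over separate fits.
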